10.4.5 ADHERENCE AND RETENTION ANALYSES

Patients will be hospitalized to receive induction therapy, and remain so until sufficient recovery permits safe hospital discharge, in accordance with standard of care. Consolidation therapy will be administered as an outpatient. Patients will be monitored as an outpatient in accordance with standard of care until recovery or study discontinuation. Study discontinuation due to adverse events, related or unrelated to study drug, will be assessed.

10.4.6 BASELINE DESCRIPTIVE STATISTICS

Planned baseline statistics include age, ethnicity, gender, genetic risk group (Philadelphia positive, Philadelphia-like, MLL rearranged, p53 mutant, etc...), baseline marrow blast burden, number of prior therapies, response to prior therapies (i.e., relapsed vs refractory), and prior exposure to selected therapeutic modalities (including allogeneic transplant, CAR T-cell therapy, blinatumomab, and inotuzumab). Demographics will be presented using summary statistics.

10.4.10 TABULATION OF INDIVIDUAL RESPONSE DATA

Responses will be presented in aggregate only.

10.4.11 EXPLORATORY ANALYSES

As previously noted, all endpoints are presently exploratory in nature, and may be used to support expansion of the present study, and/or development of a separate study.

10.5 SAMPLE SIZE

Moffitt is a high volume center for ALL, with approximately 50 new cases referred to our center yearly, of whom ~10% are anticipated to be refractory to therapy, and ~50% will relapse within 2 years of therapy. The current inclusion and exclusion criteria developed within this protocol, as well as prior enrollment to protocols targeting ALL, support a screen failure rate of less than 10%. Similarly, internal experience with CPX-351 supports a drop-out rate (ie, failure to complete induction) of less than 10%. Accordingly, we anticipate full accrual of 10 evaluable patients within 24 months.

As previously noted, this is a phase 2 pilot study designed to assess the feasibility and provide a preliminary assessment of safety and efficacy to support a more formal phase 2 study.

10.6 MEASURES TO MINIMIZE BIAS

10.6.1 ENROLLMENT

Patients with relapsed ALL will be enrolled from the Malignant Hematology clinic at the Moffitt Cancer Center. Patients will not be blinded to therapy. Given the exploratory nature of this study, stratification of patients will not be performed. Patients who are unable to complete a full course of induction may be replaced to facilitate assessment of overall remission rate.

11 SOURCE DOCUMENTS AND ACCESS TO SOURCE DATA/DOCUMENTS

The PI and other appropriate study staff are responsible for maintaining appropriate medical and research records for this trial, in compliance with ICH E6 and regulatory and institutional requirements for the protection of confidentiality of participants. Representatives of Jazz Pharmaceuticals and federal regulatory agencies may examine records for the purpose of quality assurance reviews, evaluation of the study safety, progress of the trial, and data validity.

Source documentation in both electronic and paper form shall be retained for at least two years after the final closure of the trial. These include hospital records, clinical research subject charts (with paper AE logs), research laboratory notes, electronic CRFs, and pharmacy dispensing records.

12 QUALITY ASSURANCE AND QUALITY CONTROL

Quality control procedures will be implemented beginning with the OnCore data entry system and data QC checks that will be run on the database will be generated. Any missing data or data anomalies will be communicated to the staff for clarification/resolution.

Following written SOPs, the Moffitt internal monitors will verify that the clinical trial is conducted and data are generated, documented (recorded), and reported in compliance with the protocol, GCP, and the applicable regulatory requirements (e.g., good laboratory practices (GLP), good manufacturing

practices (GMP)).

The investigational site will provide direct access to source data/documents, and reports for the purpose of monitoring and auditing, and inspection by local and regulatory authorities.

All staff will be trained by the PI through a site initiation presentation, power point training for training on the initial protocol for those staff unable to attend the initiation presentation, and ongoing self-study as protocol amendments are approved. Training will be documented on a signature log that will be filed in the electronic regulatory binder.

13 ETHICS/PROTECTION OF HUMAN SUBJECTS

13.1 ETHICAL STANDARD

The investigator will ensure that this study is conducted in full conformity with Regulations for the Protection of Human Subjects of Research codified in 45 CFR Part 46, 21 CFR Part 50, 21 CFR Part 56, and/or the ICH E6.

13.2 INSTITUTIONAL REVIEW BOARD

The protocol, informed consent form(s), recruitment materials, and all participant materials will be submitted to the IRB for review and approval. Approval of both the protocol and the consent form must be obtained before any participant is enrolled. Any amendment to the protocol will require review and approval by the IRB before the changes are implemented to the study. All changes to the consent form will be IRB approved; a determination will be made regarding whether previously consented participants need to be re-consented.

13.3 INFORMED CONSENT PROCESS

13.3.1 CONSENT/ASSENT AND OTHER INFORMATIONAL DOCUMENTS PROVIDED TO PARTICIPANTS

Consent forms describing in detail the study agent, study procedures, and risks will be given to the participant and written documentation of informed consent will be required prior to starting intervention/administering study product.

13.3.2 CONSENT PROCEDURES AND DOCUMENTATION

Informed consent is a process that is initiated prior to the individual's agreeing to participate in the study and continues throughout the individual's study participation. Extensive discussion of risks and possible benefits of participation will be provided to the participants and their families. Consent forms will be IRB-approved and the participant will be asked to read and review the document. The investigator will explain the research study to the participant and answer any questions that may arise. All participants will receive a verbal explanation in terms suited to their comprehension of the purposes, procedures, and potential risks of the study and of their rights as research participants. Participants will have the opportunity to carefully review the written consent form and ask questions prior to signing.

The participants should have the opportunity to discuss the study with their surrogates or think about it prior to agreeing to participate. The participant will sign the informed consent document prior to any

procedures being done specifically for the study. The participants may withdraw consent at any time throughout the course of the trial. A copy of the informed consent document will be given to the participants for their records. The rights and welfare of the participants will be protected by emphasizing to them that the quality of their medical care will not be adversely affected if they decline to participate in this study.

13.4 PARTICIPANT AND DATA CONFIDENTIALITY

Participant confidentiality is strictly held in trust by the participating investigators, their staff, and the sponsor and their agents. This confidentiality is extended to cover testing of biological samples and genetic tests in addition to the clinical information relating to participants. Therefore, the study protocol, documentation, data, and all other information generated will be held in strict confidence. No information concerning the study or the data will be released to any unauthorized third party without prior written approval of the sponsor.

The Moffitt study monitor, other authorized representatives of Moffitt, representatives of the IRB or pharmaceutical companies supplying study products may inspect all documents and records required to be maintained by the investigator, including but not limited to, medical records (office, clinic, or hospital) and pharmacy records for the participants in this study. The clinical study site will permit access to such records.

The study participant's contact information will be securely stored at each clinical site for internal use during the study. At the end of the study, all records will continue to be kept in a secure location for as long a period as dictated by local IRB and Institutional regulations.

Study participant research data, which is for purposes of statistical analysis and scientific reporting, will be transmitted to and stored at Moffitt. This will not include the participants' contact or identifying information. Rather, individual participants and their research data will be identified by a unique study identification number. The study data entry and study management systems used by clinical sites and by Moffitt research staff will be secured and password protected. At the end of the study, all study databases will be de-identified and archived at the Moffitt.

13.4.1 RESEARCH USE OF STORED HUMAN SAMPLES, SPECIMENS, OR DATA

Evaluation of correlative biomarkers will be performed on fresh tissue, with the exception of PLD1 immunohistochemistry. Patients consenting to the TCC platform may have additional unused material archived for future use – however, this will occur outside the context of this protocol, and will be governed independently.

A database will be created to store the clinical and analytical data for this project. This database will be located on a password-protected hard drive, and additionally, the database will be itself password-protected to ensure maximal security with regards to maintained privacy of patient-related information. Specific information included in this database will entail patient name, age, gender, medical record number, clinical diagnosis, molecular phenotype, treatment history, and survival. Database access will be limited to the PI and Co-PIs described above.

Patients will be selected according to established inclusion criteria as identified above. Patients will be identified primarily according to clinical documentation of disease status

included in clinical notes contained in the patient record; however, appropriate patients may also be identified in the context of clinical evaluation up front with names and medical record numbers **referred to** prior to scheduling the bone marrow biopsy procedure to facilitate sample identification and collection.

13.5 FUTURE USE OF STORED SPECIMENS

Data collected for this study will be analyzed and stored at the Moffitt Cancer Center. Permission to transmit data will be included in the informed consent.

For patients consenting to the Moffitt Total Cancer Care (TCC) protocol, de-identified biological samples will be stored within the Moffitt TCC biosample repository with the same goal as the sharing of data with Jazz Pharmaceuticals. These samples could be used for research into the causes of acute lymphoblastic leukemia, its complications and other conditions for which individuals with acute lymphoblastic leukemia are at increased risk, and to improve treatment. The Moffitt TCC biosample repository will also be provided with a code-link that will allow linking the biological specimens with the phenotypic data from each participant, maintaining the masking of the identity of the participant.

During the conduct of the study, an individual participant can choose to withdraw consent to have biological specimens stored for future research. However, withdrawal of consent with regard to biosample storage will not be possible after the study is completed.

When the study is completed, access to study data and/or samples will be provided through the Moffitt TCC repository.

14 DATA HANDLING AND RECORD KEEPING

14.1 DATA COLLECTION AND MANAGEMENT RESPONSIBILITIES

Data collection is the responsibility of the clinical trial staff at the site under the supervision of the site PI. The PI is responsible for ensuring the accuracy, completeness, legibility, and timeliness of the data reported.

All source documents should be completed in a neat, legible manner to ensure accurate interpretation of data. Black ink is required to ensure clarity of reproduced copies. When making changes or corrections, cross out the original entry with a single line, and initial and date the change. All paper source documents will be scanned into the electronic medical record of each subject for storage. **DO NOT ERASE, OVERWRITE, OR USE CORRECTION FLUID OR TAPE ON THE ORIGINAL.**

Copies of the electronic CRF (eCRF) will be provided for use as source documents and maintained for recording data for each participant enrolled in the study. Data reported in the eCRF derived from source documents should be consistent with the source documents or the discrepancies should be explained and captured in a progress note and maintained in the participant's official electronic study record.

Clinical data (including AEs, concomitant medications, and expected adverse reactions data) and clinical laboratory data will be entered into OnCore, a 21 CFR Part 11-compliant data capture system provided by Moffitt. The data system includes password protection and internal quality checks, such as automatic range checks, to identify data that appear inconsistent, incomplete, or inaccurate. Clinical data will be entered directly from the source documents.

14.2 STUDY RECORDS RETENTION

Study documents should be retained for a minimum of 2 years after the last approval of a marketing application in an ICH region and until there are no pending or contemplated marketing applications in an ICH region or until at least 2 years have elapsed since the formal discontinuation of clinical development of the drug combination studied in this protocol. No records will be destroyed without the written consent of the sponsor, if applicable.

14.3 PROTOCOL DEVIATIONS

A protocol deviation is any noncompliance with the clinical trial protocol, GCP, or MOP requirements. The noncompliance may be either on the part of the participant, the investigator, or the study site staff. As a result of deviations, corrective actions are to be developed by the site and implemented promptly.

These practices are consistent with ICH E6:

- 4.5 Compliance with Protocol, sections 4.5.1, 4.5.2, and 4.5.3
- 5.1 Quality Assurance and Quality Control, section 5.1.1
- 5.20 Noncompliance, sections 5.20.1, and 5.20.2.

It is the responsibility of the site to use continuous vigilance to identify and report deviations as defined by the Moffitt Clinical Trials Office standard. All deviations must be addressed in study source documents. Protocol deviations must be sent to the local IRB per their guidelines. The site PI/study staff is responsible for knowing and adhering to their IRB requirements.

14.4 PUBLICATION AND DATA SHARING POLICY

The International Committee of Medical Journal Editors (ICMJE) member journals have adopted a clinical trials registration policy as a condition for publication. The ICMJE defines a clinical trial as any research project that prospectively assigns human subjects to intervention or concurrent comparison or control groups to study the cause-and-effect relationship between a medical intervention and a health outcome. Medical interventions include drugs, surgical procedures, devices, behavioral treatments, process-of-care changes, and the like. Health outcomes include any biomedical or health-related measures obtained in patients or participants, including pharmacokinetic measures and adverse events. The ICMJE policy, and the Section 801 of the Food and Drug Administration Amendments Act of 2007, requires that all clinical trials be registered in a public trials registry such as ClinicalTrials.gov, which is sponsored by the National Library of Medicine.

The PI will provide to the Protocol Information Specialist at Moffitt Cancer Center, details as requested for registering and reporting results for this clinical trial on ClinicalTrials.gov. At the conclusion of the trial, the PI will make study results available to the research community and the public-at-large.

Authorship in publications will be determined by the PI depending on participation, enrollment, and significant contribution during the trial process and manuscript elaboration.

15 CONFLICT OF INTEREST POLICY

The independence of this study from any actual or perceived influence, such as by the pharmaceutical industry, is critical. Therefore any actual conflict of interest of persons who have a role in the design, conduct, analysis, publication, or any aspect of this trial will be disclosed and managed. Furthermore, persons who have a perceived conflict of interest will be required to have such conflicts managed in a way that is appropriate to their participation in the trial. The study leadership and the Moffitt Cancer Center have established policies and procedures for all study group members to disclose all conflicts of interest and will establish a mechanism for the management of all reported dualities of interest.

APPENDIX

Appendix A Response Criteria

Complete remission (CR) ^a	Bone marrow blasts <5%; absence of blasts with Auer rods; absence of extramedullary disease; absolute neutrophil count >1.0 x 10 ⁹ /L (1000/μL); platelet count >100 x 10 ⁹ /L (100,000/μL); independence from red cell transfusions
CR with incomplete recovery (CRi) ^b	All CR criteria except for residual neutropenia (<1.0 x 10 ⁹ /L [1000/μL]) or thrombocytopenia (<100 x 10 ⁹ /L [100,000/μL])
Partial Response (PR)	Greater than 50% decrease in blasts, and/or decrease to less than 25% blasts with recovery of neutrophils (>1.0 x 10 ⁹ /L), and platelets (>100 x 10 ⁹ /L)
Persistent Disease (PD)	Failure to achieve CR or CRi; only includes patients surviving ≥7 days following completion of initial treatment, with evidence of persistent leukemia (blasts in peripheral blood, extramedullary leukemia, or persistence in the bone marrow)
Relapse ^c	Bone marrow blasts ≥5%; or reappearance of blasts in the blood after achievement of a CR or CRi; or development of extramedullary disease

^a Bone marrow assessment required to confirm CR. All criteria need to be fulfilled; marrow evaluation should be based on a count of 200 nucleated cells in an aspirate with spicules; if ambiguous, consider repeat exam after 5 to 7 days; flow cytometric evaluation may help to distinguish between persistent leukemia and regenerating normal marrow; a marrow biopsy should be performed in cases of dry tap, or if no spicules are obtained; no minimum duration of response required.

^b Bone marrow assessment required to confirm CRi. Some patients may not achieve complete hematologic recovery prior to initiation of consolidation. CRi cannot be declared earlier than Day 35 to allow adequate time for documentation of peripheral blood recovery. Consolidation may begin no earlier than 35 days after the last induction course.

^c In cases with low blast percentages (5-10%), a repeat marrow should be performed to confirm relapse. Appearance of new dysplastic changes should be closely monitored for emerging relapse. In a patient who has been recently treated, dysplasia or a transient increase in blasts may reflect a chemotherapy effect and recovery of hematopoiesis.

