4.2 STUDY ENDPOINTS

4.2.1 PRIMARY ENDPOINT

- We will measure remission rate at day 28 to address the primary endpoint of complete remission (with or without complete hematologic recovery), as defined by Cheson Criteria (ref 27). For those with extramedullary disease, Lugano criteria will be used to assess response (ref 32). This is a standard assessment of drug efficacy for phase 2 clinical trial design in acute leukemias, as response correlates closely with progression free- and overall survival (PFS and OS).

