5 STUDY ENROLLMENT AND WITHDRAWAL

5.1 PARTICIPANT INCLUSION CRITERIA

Patients must meet all of the following criteria to be eligible for study entry:

1. Be willing and able to provide written informed consent/assent for the trial.
2. Be ≥ 18 years of age on day of signing informed consent.
3. Able to adhere to the study visit schedule and other protocol requirements.
4. Pathologically confirmed B- or T-cell acute lymphoblastic or mixed phenotype acute leukemia, with $\geq 5\%$ peripheral blood or bone marrow lymphoblasts and/or extramedullary disease $>1 \times 1 \text{ cm}$.
5. Relapsed or refractory acute lymphoblastic leukemia after at least 1 prior cycle of therapy. Patients with Philadelphia chromosome positive disease must have failed at least two prior tyrosine kinase inhibitors.
6. Eastern Cooperative Oncology Group (ECOG) performance status 0-1.
7. Cardiac ejection fraction $\geq 50\%$ by echocardiography or MUGA.
8. Must be at least 2 weeks out from any prior systemic chemotherapy, blinatumumab, radiation, and/or other investigational agents, and have recovered to grade 1 from any toxicity related to prior therapy. Glucocorticoids are permitted up to 1 day prior to the first dose.
9. Serum bilirubin and creatinine $\leq 1.5 \times$ upper limit of normal (ULN). AST and ALT must be $\leq 3 \times$ ULN, unless there is suspected liver involvement.
10. Females of childbearing potential (FCBP) must have a negative serum pregnancy test at screening. A FCBP is considered when a sexually mature female: 1) has not undergone a hysterectomy or bilateral oophorectomy; or 2) has not been naturally postmenopausal for at least 12 consecutive months.
11. A FCBP must agree to use of two methods of highly effective contraception, be surgically sterile, or abstain from heterosexual activity for the course of the study through 30 days after the last dose of study treatment.
12. Male subjects must agree to use an adequate method of contraception starting with the first dose of study therapy through 30 days after the last dose of study therapy. Men must agree to not donate sperm during and after the study

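### As written out in Appendix A, CR and CRi do not require blood to be clear of lymphoblasts, so circulating leukemia can be scored as response

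*Combined protocol and SAP*

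**What the plan says.** - **Primary endpoint (Section 4.2.1).** Day-28 "complete remission (with or without complete hematologic recovery), as defined by Cheson Criteria (ref 27"). Section 10.2 likewise names CR and CRi together as the primary endpoint.
- **CR (Appendix A).** The row starts "Bone marrow blasts <5%; absence of blasts with Auer rods; absence of extramedullary disease; absolute neutrophil count" and ends with the neutrophil and platelet thresholds and freedom from red cell transfusion. Footnote a adds "All criteria need to be fulfilled; marrow evaluation should be based on a count of 200 nucleated cells in an aspirate with spicules"; the rest of that footnote also concerns the marrow and response duration.
- **CRi (Appendix A).** "All CR criteria except for residual neutropenia" or thrombocytopenia. Footnote b rules out declaring CRi before Day 35.
- **Persistent Disease (Appendix A).** It opens "Failure to achieve CR or CRi; only includes patients surviving" at least 7 days after initial treatment, and continues "with evidence of persistent leukemia (blasts in peripheral blood, extramedullary leukemia, or persistence in the bone marrow").
- **Relapse (Appendix A).** Marrow blasts of 5% or more, or "reappearance of blasts in the blood after achievement of a CR or CRi", or new extramedullary disease.
- **Entry (Section 5.1, criterion 4).** At least 5% "peripheral blood or bone marrow lymphoblasts and/or extramedullary disease" above a stated size.
- **Blood data.** Section 7.3.2.9 schedules a blood count with differential on induction day 28, but does not link it to the CR definition.

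**The concern.** The table treats blood blasts as disease in two rows and leaves them out of the row that defines response. A patient can enter on blood lymphoblasts, finish induction with marrow blasts below 5% and recovered counts, still have lymphoblasts in the blood, and meet every listed CR item. The one item about blast type, Auer rods, is a myeloid marker taken from criteria whose cited source (ref 27) is titled for acute myeloid leukemia. It does no work for B- or T-cell disease.

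The error runs one way, towards more responders. It would enter the primary CR/CRi rate, where each patient is worth 10 percentage points, and the rule of 4 responders in 10 that opens discussion of expansion. It would also remove a PFS event, because Sections 3 and 4.2.2 count non-response as one.

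**Working it through.** **1. Does any other text close the gap?**

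| Candidate text | Does it require blood clearance for CR? |
|---|---|
| CR row, no extramedullary disease | No. The Persistent Disease row lists blood blasts and extramedullary leukemia as separate items. |
| CR row, Auer rods | No. It states nothing about lymphoblasts. |
| Footnotes a and b | No. They add marrow assessment rules and the earliest date for CRi. |
| Persistent Disease row | No. It applies only when CR and CRi have not been met, so it cannot override a CR whose listed items are all satisfied. |
| Relapse row | No. The word for return implies earlier clearance, but it is not a response criterion. Blasts that never cleared do not fit it literally. |
| Sections 3 and 4.2.1 | No rule is written there. They name the marrow biopsy, imaging and the cited criteria. |

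**2. The plan's own design figures (Section 10.4.2).** Inputs: n1 = 10, r1 = 3, N = 19, r = 9, with rates 0.35 and 0.65 from Section 10.4.1.

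- Early stopping at 0.35: P(X ≤ 3 | 10, 0.35) = 0.0135 + 0.0725 + 0.1757 + 0.2522, which is 0.514 (stated 0.514).
- Average N: 10 + 9 × (1 − 0.5138) = 14.38 (stated 14.38).
- Type I error: the sum over x = 4 to 10 of P(X1 = x | 10, 0.35) × P(X2 ≥ 10 − x | 9, 0.35) = 0.0844 (stated 0.084).
- Beta: the same sum at 0.65 is 0.9048, so beta = 0.0952 (stated 0.095).

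The design reproduces, and nothing here disputes it.

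**3. Effect of misclassification.** The documents give no rate of marrow blasts below 5% with circulating lymphoblasts. Let m be the assumed share of all patients wrongly scored CR/CRi, and take the true CR/CRi rate (clearance required) as 35%. The observed rate is then q = 0.35 + m. P(at least 4 of 10) is 1 − P(X ≤ 3 | 10, q), and the 19-patient column uses the type I error sum above with q in place of 0.35.

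| m (assumed) | q | P(at least 4 of 10) | Success in the 19-patient illustration |
|---|---|---|---|
| 0 | 0.35 | 0.486 | 0.084 |
| 1% | 0.36 | 0.513 | 0.100 |
| 2% | 0.37 | 0.540 | 0.117 |
| 5% | 0.40 | 0.618 | 0.180 |

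**The case against.** **The endpoint cites an outside source.** Sections 3 and 4.2.1 define remission by the 2003 criteria, and the body text cites Appendix A only for consolidation eligibility (Sections 7.3.2.11 and 7.3.2.14). That source may contain a blood criterion, and it cannot be checked from the documents. This stands as a limit: the omission is shown for the appendix, not for the source. But the appendix is the only place where CR is written out, so it is what a reader of this protocol would apply.

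**The neighbouring rows show the intent.** Persistent Disease and Relapse both presuppose clearance, and an investigator would probably refuse CR to a patient with visible blood leukemia. That is fair, and it is a reason to write the rule down rather than leave the primary endpoint of an open-label single-arm trial to judgment.

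**The stakes are modest.** Section 10.2 calls every endpoint exploratory, the two-stage table is offered as an illustration, and 4 of 10 leads only to consideration of more funding. This stands and limits the weight of the point. Day-28 MRD is a partial cross-check, but it is a secondary endpoint and does not change who is scored CR.

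**A strict blood rule could create false non-responders.** Footnotes a and c warn about regenerating marrow and transient blasts after treatment, and Section 7.4 gives growth factor to all patients. This stands, and any added criterion needs a route for equivocal cells.

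**Conclusion.** The gap is real in the text. Applied literally, Appendix A lets a patient with circulating lymphoblasts count as CR or CRi and avoid the non-response event in PFS. It is worth correcting because the bias has one direction and the repair is small. Its size is unknown and probably small: 0.486 becomes about 0.51 to 0.62 for assumed misclassification of 1% to 5%, taking a true rate of 35% and independent patients.

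Three stronger readings are tempting and are not supported:

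- **That such a patient could fail PFS only through marrow or extramedullary relapse.** Death is also a PFS event in Sections 3 and 4.2.2.
- **That one false responder lifts the chance of meeting the 4-of-10 rule from 0.486 to 0.663.** The second figure, P(X ≥ 3 | 9, 0.35), assumes that the case has already occurred, while the first does not. The like-for-like conditional contrast is P(X ≥ 4 | 9, 0.35) = 0.391 against 0.663, and it still presumes the event.
- **That the day-28 blood count alone would settle the matter.** Footnote b does not allow CRi before Day 35.

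**What to change.** For scoring the primary endpoint, add to the CR row, and so to CRi: *no circulating leukemic lymphoblasts on the CBC differential used for the response determination (day 28, or the later date on which CRi is declared)*. State that equivocal cells are resolved by the repeat examination or flow cytometry that footnote a already allows. Keep the Auer-rod item for mixed phenotype leukemia, which criterion 4 admits.

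Align the Persistent Disease and Relapse rows so that blood blasts are handled the same way in all of them. Have Sections 3 and 4.2.1 point to Appendix A as the operative definition.

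CR/CRi also appears in the consolidation criteria (Sections 6.1.9, 7.3.2.11 and 7.3.2.14). The sponsor must reconcile those sections with the revised row; this point takes no position on what the treatment rule should be.

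Cost: a short phrase, two aligned rows and that reconciliation. No new type of test is needed, since CR and CRi already depend on blood counts and a differential is scheduled on day 28. The CR/CRi rate may come out slightly less favourable.
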